2.17 Are there any planned subgroup analyses?

A priori, we plan to explore 5 sources of potential heterogeneity:

- 1) Age
- 2) Severity of burn as judged by TBSA, SOFA, and APACHE.
- 3) Presence of trauma and traumatic brain injury
- 4) Adequacy of prior care/resuscitation as judged by direct arrival vs. transfer from other setting with some prior care.
- 5) early vs. delayed initiation of study IP (based on the observed distribution of times to start study IP).

The rationale for these subgroups is that older patients and patients with more severe burns and more severe trauma will likely be more deficient in vitamin C and, therefore, more likely to benefit from supplementation.^{88,89} As we suspect that earlier treatment with vitamin C, particularly during the resuscitative period, will have the potential for a greater treatment effect, we will explore this source of heterogeneity. The statistical significance of apparent effect modification will be assessed by testing a treatment by covariate interaction term using modified Poisson for mortality and the Cox PH model for time to discharge alive as described above. Due to the increased risk of type I and type II error, subgroup-specific inferences will be considered

exploratory and hypothesis generating. Subgroup-specific effects will be presented by forest plots based on TBSA tertiles and presence of non-thermal trauma, but modelling and tests for interaction will keep TBSA as continuous.

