2.5 What are the planned Inclusion/Exclusion criteria?

Inclusion criteria 18 years of age or older with deep 2nd and/or 3rd degree burns, who are assessed as requiring skin grafting, and a minimum burn size $\geq 20\%$ Total Body Surface Area (TBSA). Patients with smaller burns are less likely to require fluid resuscitation and their risk of morbidity and mortality is lower. Burn size will be determined by the attending physician (and confirmed by the attending surgeon if it is not the same person).

Exclusion criteria

1. >24 hours from admission to participating hospital to consent.
2. Patients admitted to burn unit >24 hours from injury or accident.
3. Patients who are moribund (not expected to survive the next 72 hours).
4. Pregnancy (pregnancy will be ruled out as part of standard of care) or lactating.
5. Enrolment in another industry sponsored ICU interventional study
6. Receiving high-dose IV vitamin C already (enteral or oral vitamin C is allowed).
7. Known glucose-6-phosphate dehydrogenase (G6PD) deficiency.
8. Recent history of kidney stones (within the last year).
9. Concomitant use of hydroxocobalamin (vitamin B12) for suspected cyanide poisoning.

These criteria are designed to include those severe burn injury patients who are likely to benefit from the therapeutic intervention tested in this trial. For the nutrients to have a beneficial effect, particularly on resuscitation outcomes, they have to be delivered as soon after the injury as possible (ideally within 3- 6 hours of admission). However, we acknowledge that it will require some time for research staff to obtain informed consent. We will exclude patients not likely to benefit from the intervention (not likely to survive beyond 72 hours) or those in whom the safety of high dose intravenous vitamin C is uncertain (pregnant patients and patients with G6PD deficiency). High dose vitamin C appears safe in kidney disease except for patients who may have had recent kidney stones or who have received vitamin B12 since it excretes oxalate acid in the kidneys as well. Consistent with other trials of high dose vitamin C, we will recruit patients with kidney injury or failure but exclude patients with recent history of kidney stones.

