VASOPRESSORS and INOTROPES (record from ACU admission to ACU discharge for a maximum of 3 months)												
Vasopressors/Inotropes (highest hourly rate) for each: dobutamine, dopamine, epinephrine, levosimendan, milrinone, norepinephrine, phenylephrine, vasopressin.												
VITAMIN C DOSING (record all doses received)												

SCHEDULE OF ASSESSMENTS	Screening / Baseline Day 1	Day 2	Day 3	Day 4	Day 5	Day 6	Day 7	Day 8	Ad Hoc	Outcomes (d/c to 90 days max)	6 Month Follow-Up	Early withdrawal
Vitamin C administration (start/stop times; volume infused; interruptions)												
DAILY LABORATORY (record labs ordered as SOC from ACU admission to 3 days after last dose of IP)												
Creatinine, serum (highest)												
Bilirubin, Total (highest)												
Urea (highest)												
Glucose (closest to 8:00 A.M.)												
Hypoglycemic events (record up to 3/day)												

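### Section 2.17 frames the exploratory timing modifier as an early/delayed split at an unnamed, data-derived cut and keeps only TBSA continuous for interaction tests; delay should be tested as continuous too

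*Combined protocol and SAP*

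**What the plan says.** Section 2.17 names five sources of heterogeneity to explore. The fifth is "early vs. delayed initiation of study IP (based on the observed distribution of times to start study IP". No cut-point, quantile or time origin is given.

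The reason offered is directional: "As we suspect that earlier treatment with vitamin C, particularly during the resuscitative period, will have the potential for a greater treatment effect". Section 2.5 says of the study nutrients that "they have to be delivered as soon after the injury as possible (ideally within 3- 6 hours of admission".

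On testing, section 2.17 states: "The statistical significance of apparent effect modification will be assessed by testing a treatment by covariate interaction term using modified Poisson for mortality", with a Cox model for time to discharge alive. TBSA tertiles are used in the forest plots, but "modelling and tests for interaction will keep TBSA as continuous". No other modifier is mentioned in that sentence. On status, the section says: "Due to the increased risk of type I and type II error, subgroup-specific inferences will be considered" exploratory and hypothesis generating.

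The data for a continuous delay are collected. Appendix B records the date and time of the burn, the hospital and unit admission times, and "Vitamin C administration (start/stop times; volume infused; interruptions".

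**The concern.** Time to first dose is a continuous quantity, and the entry rules let it vary widely. Section 2.5 allows up to 24 hours from injury to burn-unit admission, and excludes a patient only if it is ">24 hours from admission to participating hospital to consent". For TBSA the plan separates what is displayed from what is tested. For timing it describes only the two groups. If those groups enter the interaction term, all variation in delay within each group is discarded.

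Interaction tests are weak to begin with, and section 2.17 itself acknowledges the raised risk of type II error. Splitting the modifier weakens the test further for no gain in data collection. A cut taken from the observed start times also has no fixed meaning in hours until enrolment is complete, and it need not fall near the 3-6 hours from admission that section 2.5 calls ideal.

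**Working it through.** **The plan's own figure.** The documents state no power for any interaction, so the check starts from the primary outcome in section 2.10: 333 per arm, 27% vs 18%, two-sided alpha 0.05, power 78%.

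- SE of log RR = sqrt(0.73/(333×0.27) + 0.82/(333×0.18)) = 0.148.
- |log RR| = ln 1.5 = 0.405, so z = 2.75 and power = Φ(2.75 − 1.96) = 78.4%.
- The two-proportion formula gives 79.6%.
- Simulation with the RR > 1.1 stopping rule at n = 222 and n = 444 gives 78.8%.
- Simulated stopping under the null is 33.2% and 8.0%, against 33.3% and 8.0% in Appendix C.

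The plan's figure reproduces.

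**Information kept by a split.** For an interaction linear in delay, the fraction kept is the squared correlation between delay and its indicator:

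r² = q(1−q) × (mean above cut − mean below cut)² / variance, where q is the cut quantile.

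At the median (q = 0.5):

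- Uniform over width w: 0.25 × (w/2)² / (w²/12) = 0.75.
- Normal: 0.25 × (2 × 0.798)² = 0.64.
- Lognormal, log-SD 0.5: 0.52.

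| Assumed delay | Information lost, median split | 80% power becomes | 50% power becomes |
|---|---|---|---|
| Uniform | 25% | 68% | 40% |
| Normal | 36% | 61% | 35% |
| Lognormal, log-SD 0.5 | 48% | 52% | 29% |

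Power = Φ(ncp × r − 1.96), with ncp = 2.80 for 80% power and 1.96 for 50%. For example, uniform: Φ(2.80 × 0.866 − 1.96) = 68%.

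**Other shapes and cuts.** Median-split losses are 39-44% for an exponential delay truncated at 24 h (scale 8 or 6 h), 52% for an untruncated exponential and 60% for a lognormal with log-SD 0.75. Moving the cut to a tertile or quartile gives 33% or 44% (uniform) and 41% or 46% (normal). Skewed shapes range from about 27% to over 75%, depending on which side the cut falls.

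**Simulation check.** Modified Poisson with robust standard errors, n = 666, control rate 27% (the composite outcome), mean RR 0.667, assumed log-RR slope 0.3 per SD of delay, 2,000 runs each. Power, continuous vs median split:

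- uniform: 51% vs 39%
- normal: 56% vs 37%
- truncated exponential, scale 8 h: 62% vs 39%

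Null rejection in these three cases was 5.1-6.0% for the continuous term and 4.4-5.3% for the split, so about a point of the difference may reflect size.

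**Time to discharge alive.** Assume 85% of 666 are discharged alive and delay is uniform over 2-24 h. For a ratio R of subdistribution hazard ratios between the two ends, ncp = (ln R / √12) × sqrt(0.85 × 666 / 4).

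- R = 2: 66% continuous vs 54% split.
- R = 1.5: 29% vs 23%.
- R = 1.32: 16% vs 13%.

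**If the effect is a step.** The squared correlation is symmetric. A step exactly at the median costs the linear term the same 25%, 36% or 48%. A step elsewhere can reverse this. With delay uniform over 2-24 h and a step at 6 h (p = 4/22 = 0.18), the linear term keeps 3p(1−p) = 45%, while the median split keeps (0.5p)² / (0.25 × p(1−p)) = 22%.

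**The case against.** The strongest reply is that the plan never says delay enters the test as a binary term. The TBSA sentence exists because the forest plots use TBSA tertiles, and it is equally silent about age, SOFA and APACHE. This stands to a degree: the binary test is an inference. But timing is the only modifier measured on a continuum that the list itself presents as two groups, so the inference is the natural one. If continuous delay was intended, the same sentence is needed to say so.

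Second, the rationale singles out the resuscitative period, and section 2.5 speaks of a window. Both are compatible with a threshold effect, for which two groups could be efficient. That is fair, and the loss to a linear term from a step exactly at the cut would not be small. It does not rescue a cut chosen from the observed distribution, which has no reason to coincide with such a threshold.

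Third, where the interaction is modest, the test is weak on either scale. In the discharge example the gain is 6 points at a ratio of 1.5 and 3 points at 1.32. This also stands and limits the importance of the point.

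A reader might also infer that the cut is outcome-driven or that the results could never be pooled. Neither follows. The cut uses start times rather than outcomes, and recorded start times allow re-analysis on any scale.

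**Conclusion.** The point holds as a minor, inexpensive improvement. As written, section 2.17 points to testing the timing interaction on a dichotomised delay, while applying the better practice to TBSA alone. Under a median split and an effect roughly linear in delay, the loss of information for that test is about 25% with uniform delay and rises to 50% or more with strongly right-skewed delay.

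Three stronger readings should be avoided:

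- No particular percentage is a property of the plan. The documents supply no delay distribution, cut quantile or effect shape, and 48% is not an upper bound.
- The plan does not commit in words to a binary test.
- Timing is not singled out as the key hypothesis. It is the fifth of five exploratory modifiers, and neither the primary analysis nor its 78% power is touched.

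**What to change.** In section 2.17:

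- Redefine item 5 as time to first dose of study product, in hours, from one stated origin. Injury is a candidate because Appendix B already records it. Note that the 3-6 hours in section 2.5 is counted from admission, so the origin must be explicit.
- Extend the closing sentence so that time to first dose, like TBSA, stays continuous in interaction models and tests.
- Pre-specify a restricted cubic spline, with its knots, to examine non-linearity.
- Use early/delayed categories for the forest plot only, and state the cut rule in advance.

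The cost is a few lines of text, with no new data and no extra patients. The downside is that a true step exactly at the chosen cut would be tested less efficiently by the linear term, by an amount similar to the loss described above. The spline would help reveal such a shape but would not recover all of that efficiency.

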2.7 What is the proposed duration of follow-up?

Patient clinical status will be monitored daily during the acute care unit stay for up to 3 days after termination of study IP (maximum 7 days). Hospital outcomes will be abstracted from the chart once the patient is discharged.

2.8 and 2.9 What are the proposed primary and secondary outcome measures?

The primary outcome for this phase III trial is persistent organ dysfunction (POD)+death at 28 days, a novel composite endpoint that combines being alive and being free of organ support (inotropes or vasopressors or mechanical circulatory assistance, renal replacement therapy and mechanical ventilation).⁷⁷

The most important secondary endpoint of this trial will be “time to discharge alive from hospital.” The other secondary outcomes will be the components of 28-day POD which include mortality, use of inotropes or vasopressors or mechanical circulatory assistance, renal replacement therapy and mechanical ventilation and POD-free days in the first 28 days.

Tertiary outcomes will include intensive care unit (ICU) outcomes (e.g. length of stay, duration of mechanical ventilation, and readmission rates); hospital outcomes (hospital mortality, length of stay, bacteremia with gram-negative bacilli, and readmission rates); and 6-month outcomes (mortality, health related quality of life and physical function domain of the Short Form-36 (SF-36) questionnaire, activities of daily living and instrumental activities of daily living). We will also record frequency of operative procedures for burn care, presence of inhalation injury, blood transfusions, and other major cost drivers to support our economic evaluation.

2.10 What is the proposed sample size and what is the justification for the assumptions underlying the power calculation?

The primary outcome for this trial is PODS+death at 28 days after randomization. Based on estimates from currently available pooled data from the RE-ENERGIZE study with $\geq 20\%$ TBSA (n=539), we estimate that the 28-day PODS rate will be 27%. Based on our simulations accounting for two interim analyses (see Tables in Appendix C), we estimate that with 333 subjects per arm, we would achieve 78% power to observe a reduction at a one-sided alpha of 0.025 (or two-sided alpha=0.05) if the rate of PODS at 28 days was reduced from 27% to 18% (RRR=33.3%).

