Given the 30-36% relative risk reduction in mortality observed in the meta-analysis reported in section 1.2, we believe this treatment effect to be plausible. The simulated power under various effect sizes accounting for the interim analyses is provided in Appendix C. Based on our several prior studies in this field, we expect to obtain the 28-day PODS status on virtually all patients. Since the randomization is stratified by site and the analysis will control for site, the possible presence of between-site heterogeneity in overall rates will not decrease the power, assuming that the effect of treatment is consistent across sites.

A sample size of 666 patients also provides adequate power for one of our key secondary outcomes, time to discharge from hospital alive. Based on estimates from currently available pooled data from the RE-ENERGIZE study with $\geq 20\%$ TBSA (n=539), we estimate that the median time to hospital discharge is 47 days, by which time no more than 10% would have died. We consider death a competing risk precluding live hospital discharge and, for this outcome, conservatively assume that the intervention has no effect on mortality. With 333 patients per arm followed for up to 182 days and allowing for 5% loss to follow-up, we would achieve 90% power at a two-sided alpha of 0.05 to compare the cumulative incidence of time to alive hospital discharge over 6 months, if the subdistribution hazard ratio of time to live discharge was 1.32. Assuming time to discharge follows an exponential distribution except allowing for the competing risk of death, this effect size would equate to 60% vs. 50% of patients being

discharged alive by day 47 in the intervention and control arm respectively. However, power will decrease due to the interim analysis. The interim analysis will reduce the power by 1% if the RR for PODS+death is 0.667 and the power for time to discharge alive will remain above 80% if the RR of PODS+death is less than 0.85.

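### Section 2.17 specifies interaction tests for mortality and time to discharge alive, but none for the primary outcome, 28-day POD+death

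*Combined protocol and SAP*

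**What the plan says.** Sections 2.8 and 2.9 state: "The primary outcome for this phase III trial is persistent organ dysfunction (POD)+death at 28 days". They rank time to discharge alive as the leading secondary outcome and continue: "The other secondary outcomes will be the components of 28-day POD which include mortality". Hospital and 6-month mortality are tertiary.

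Section 2.16 analyses the primary outcome by modified Poisson regression with robust standard errors clustered by site, adjusted for burn size, traumatic brain injury, baseline ventilation and injury severity score. Binary secondary outcomes get the same model. Six-month mortality is assigned to Kaplan-Meier and Cox methods, and tertiary outcomes get no p-values.

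Section 2.17 lists five sources of heterogeneity: age, burn severity, trauma and brain injury, prior care, and timing of study product. Effect modification is to be assessed by "testing a treatment by covariate interaction term using modified Poisson for mortality and the Cox PH model for time to discharge alive". Forest plots are planned by burn-size tertile and non-thermal trauma, with no outcome named. Subgroup inferences are labelled exploratory.

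**The concern.** A subgroup section normally asks first whether the primary treatment effect varies. Here the modified Poisson model, introduced in 2.16 for POD+death, is attached in 2.17 to only one component of that composite.

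The question matters for this trial. Section 1.3 reports a possible subgroup difference favouring sicker populations in the latest meta-analysis (p=0.06) and treats benefit in lower-mortality burn patients as unresolved. Without a named test on POD+death, the report would either be silent on whether the primary effect depends on age, severity or timing, or would rest on an analysis not fixed in the plan.

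Mortality is also undefined in 2.17. Of the time points in the plan, 28 days fits 2.16 best: 6-month mortality is analysed by Cox, and both hospital and 6-month mortality are tertiary and so reported without p-values.

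**Working it through.** **Inputs, all from section 2.10**
- 333 patients per arm, 666 in total.
- POD+death: 27% in controls, 18% under the planned effect.
- Mortality: median time to hospital discharge is 47 days, "by which time no more than 10% would have died". This is the only planning figure for deaths; 28-day mortality cannot exceed it.
- Time to discharge alive: subdistribution hazard ratio 1.32 with 90% power; 50% vs 60% discharged alive by day 47.

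**Step 1. Reproduce the plan's power (78%).** Wald test on the log RR:
- SE = √[0.73/(333×0.27) + 0.82/(333×0.18)] = √(0.00812 + 0.01368) = 0.148.
- |ln(0.18/0.27)| = 0.405, and 0.405/0.148 − 1.96 ≈ 0.79, so power is 78.4% without interim analyses.
- A simulation of 200,000 trials with the RR>1.1 rule at 222 and 444 patients gives 78.7%. Under the null it stops 33.3% and 8.0% of trials at the two looks, as in Table B.

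The planning rates are therefore coherent and can be reused.

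**Step 2. Expected events**
- POD+death: 333×0.27 + 333×0.18 = 150 under the planned effect; 666×0.27 = 180 if there is no effect.
- Mortality: at most 666×0.10 = 67.
- Ratio: 150/67 = 2.2 to 180/67 = 2.7.

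**Step 3. Precision of an interaction.** On the log RR scale each cell of size n contributes (1−p)/(np). With the same cells for both outcomes, only (1−p)/p matters:
- p = 0.10: 9.00. p = 0.225 (mean of 27% and 18%): 3.44. p = 0.27: 2.70.
- Variance ratios: 9.00/3.44 = 2.6 and 9.00/2.70 = 3.3. SE ratios: 1.6 and 1.8.
- Using the two arm rates separately gives (2.70 + 4.56)/2 = 3.63 and a ratio of 9.00/3.63 = 2.5. The SE ratio still rounds to 1.6.

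**Step 4. Illustration.** Assume a 50/50 subgroup (four cells of 166.5), equal rates across cells, no adjustment and a two-sided 5% test. SE of the log ratio of RRs = √[4(1−p)/(166.5p)]. Power = Φ(|ln R|/SE − 1.96). The ratio detectable with 80% power is exp(−2.80×SE).

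| Outcome and rate | SE | Power, R=0.5 | Power, R=0.667 | Detectable R, 80% power |
|---|---|---|---|---|
| POD+death, 27% | 0.255 | 78% | 36% | 0.49 |
| POD+death, 22.5% | 0.288 | 67% | 29% | 0.45 |
| Mortality, 10% | 0.465 | 32% | 14% | 0.27 |
| Mortality, 5% (assumed) | 0.676 | 18% | 9% | 0.15 |

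**Step 5. Time to discharge alive.** By Schoenfeld's formula, 90% power at a hazard ratio of 1.32 needs 4(1.96 + 1.28)²/(ln 1.32)² ≈ 546 events, or 82% of 666. By day 47 alone, the plan's rates give 333×0.50 + 333×0.60 = 366 live discharges. This outcome has many more events than POD+death.

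**The case against.** **It may be a slip.** Section 2.17 refers back to methods already described, and 2.16 introduces modified Poisson for the primary outcome, so mortality may have been written for POD+death. That is plausible, but the text does not say so, and the sentence needs correcting on either reading. The forest plots might show POD+death, but no outcome is stated and a plot is not a test.

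**The analyses are exploratory and weak in any case.** This stands. Even on POD+death, power is only 29% to 36% for a ratio of RRs of 0.667. The change makes the subgroup analyses address the right outcome; it does not make them decisive.

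**Stronger readings that the documents do not support**
- A reader might infer that all the planned interaction tests are short of events. That applies to mortality only (Step 5).
- A reader might take 10% as a firm ceiling on the deaths analysed. It is a day-47 planning bound, and 2.17 gives no time point. Deaths at 28 days would be no more than this; a longer horizon could give more.
- A reader might infer that the timing subgroup, "early vs. delayed initiation of study IP (based on the observed distribution of times to start study IP", is biased because product starts after randomisation and the cut comes from the data. The trial is double-blind and the modified ITT set contains only treated patients, so start time is unlikely to differ by arm. A cut on start times is not a cut on outcomes. Substituting time from injury to randomisation would answer a different question.

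**Conclusion.** The gap is real: no interaction test is specified for 28-day POD+death, and the binary outcome named in its place is undefined in time and less informative. At the 10% figure, mortality gives about 67 events against 150 to 180, an interaction variance about 2.6 to 3.3 times larger, and less than half the power at a ratio of RRs of 0.5 (32% vs 67% to 78%).

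These sizes rest on the plan's 27%, 18% and 10% rates and on reading mortality as 28-day mortality. The power figures also assume an even subgroup split without covariate adjustment. If 28-day mortality is below 10%, the contrast is larger. The primary estimate, its type I error and the interim rule are not affected.

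**What to change.** In section 2.17:
- Name 28-day POD+death as the first outcome for the interaction tests and for the forest plots, using the 2.16 modified Poisson model and covariates. Add the subgroup variable's main effect where 2.16 does not already include it.
- Keep time to discharge alive as the second outcome.
- If mortality is retained, state that it is 28-day mortality and treat it as supportive.
- Leave the timing subgroup as it is.

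Make the change before treatment codes are opened. It is a wording change with no new data collection. The downside is one more set of exploratory interaction tests, which the existing caution in 2.17 about type I and type II error already covers.
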